8.2 Limitations

The study design is limited by the sample size. A small difference between the two groups might therefore not result in a significant way and the study might be underpowered to draw definitive conclusions. However, all aspects of the study will be hypothesis generating, no matter of the resulting power and thereby will help to direct further investigations.

9. PUBLICATION

The findings of this study will be published by the investigators in a scientific journal and presented at scientific meetings. Also, we plan to disseminate the knowledge gained from our study via open access methods, in order to increase readership and impact. Open source publication allows readers to read publications for free and is proven to increase citations of publications.

[name] will be assigned as first and corresponding author, while [name] will be the last and senior author. The ranking of the other authors will be done in accordance to their contribution to the study.

Impact of Unexpected Death in Simulation: Skill Retention, Stress and Emotions

Data Analysis Plan

Primary Outcome: Difference in retention of non-technical crisis resource management (CRM) skills using Ottawa Global Rating Scale (OGRS)

ANCOVA:

- Dependent variable: OGRS score (total score)
- Independent variable: Death vs. survival
- Covariates: Junior vs. senior; Acute vs. non-acute

Secondary Outcome 1: Technical CRM skills (according to checklist)

- Same Videos to be provided for primary outcome will be scored using the “Task-specific checklist” (derived from American Heart Association’s Megacode Checklist) and given a score out of 18

ANCOVA:

- Dependent variable: Task-specific checklist score (total score)
- Independent variable: Death vs. survival
- Covariates: Junior vs. senior; Acute vs. non-acute

Secondary Outcome 2: Stress

Measure 1: Salivary cortisol

Five time points (minutes passed since baseline):

1. Baseline (0 minutes) during the accommodation period at the beginning of the day
2. Before scenario (10 minutes)
3. Immediately after scenario (30 minutes)
4. 30 minutes after start of scenario (45 minutes)
5. After debrief (50 minutes)

ANCOVA:

- Dependent variable: Change in cortisol concentration (versus baseline) at a given time point (for each time point)
- Independent variable: Death vs. survival
- Covariates: Junior vs. senior; Acute vs. non-acute

Regression:

- Linear regression to determine the effects of covariates (Junior vs. senior; Acute vs. non-acute) on change in cortisol concentration over time
 - Separated into “death” and “survival” groups
 - Change in cortisol concentration will be established using the baseline reading of each participant on each day of the study (time point 1).
- Unpaired t-tests will be used to compare change in cortisol levels between the “death” group and the “survival” group at each time point.

Measure 2: State-Trait Anxiety Inventory (STAI)

- Analysis will be carried out in the same way as the cortisol measures with the STAI score taking the place of the change in cortisol concentration

Measure 3: Cognitive appraisal

- Mean cognitive appraisal ratios for each group (“death” and “survival”) at each time point will be calculated and subjected to a one-sample t-test to determine whether they are significantly different from 1.
- Unpaired t-tests will be used to compare the mean ratios of the “death” and “survival” groups at each time point.

Secondary Outcome 3: Valence of emotions

Five-point Likert scale

Repeated measures ANCOVA:

- Dependent variable: Score for each emotion
- Independent variable: Death vs. survival
- Covariates: Junior vs. senior; Acute vs. non-acute
- Time points: Initial and retention

For all Outcomes:

Relationships between all outcomes (determined by ANCOVA or by Pearson’s correlation) will be presented in a matrix table.

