differ slightly in order to eliminate the potential for this recall bias described above. In summary, the scenarios are of equal complexity, but differ primarily with respect to the clinical context, initial cardiac arrest rhythm and pre-determined outcome (Appendix C).

Two well-trained confederates will act as registered nurse and as respiratory therapist within the team. These roles were prescribed to ensure standardization for each participant. The confederates will be instructed to help and to perform tasks when directed but not to offer crisis management advice or differential diagnoses. An individualized, video-assisted, instructor-led, structured debriefing lasting 30 minutes will follow the initial scenario. As suggested by Gaba, highly experienced and well prepared instructors will lead the debriefing phase in order to deal with potential upcoming emotions and issues.¹⁹ All scenarios and debriefings will be video recorded for performance analysis.

Retention Test

Previous data have shown that, even with high-fidelity simulation, resuscitation knowledge and skills deteriorate between as early as 2 weeks and 1 year after the learning intervention, with a faster decay in skill.^{21,22} Therefore a retention test is planned 3 months after the initial test. After a short accommodation phase of 15 minutes and assessment of baseline data a standardized scenario briefing will be done. Participants from both groups will be asked to be team-leader in a cardiac arrest scenario to test for skill retention. Again, two confederates, one acting as registered nurse and one acting as respiratory therapist will be team members. While the scenarios will be the same as in the initial test, the case presentation of the scenario and the mannequin “outcome” will be switched for the retention test. The mannequin will survive for the “unexpected death” group and it will die in the “survive” group. That way, each participant will be exposed to simulation death in the study once. To maximize learning opportunities for participants in this study, an individualized debriefing with a specially trained facilitator will follow the retention test as well.

All scenarios and debriefings will be video recorded for further performance analysis.

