7. ANALYSIS

7.1 Quantitative analysis

7.1.1 Primary outcome parameter

The difference in retention of non-technical skills for crisis management between the intervention and the control group (measured by the Ottawa Global Rating), specified as the difference in performance between the initial and the retention test, will be our primary outcome.

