7.3 Statistical analysis

As it has been suggested as best practice for stratified randomized controlled trials, ANCOVA will be used to analyze the outcome parameters using the level of training (PGY1-3 vs PGY 4-5 and fellows) and specialities (acute care specialities vs. non-acute care specialities) as covariates.³⁵ Group assignment (unexpected death, alive) will be used as the independent variable. Demographic data will be analyzed using an unpaired Student's *t*-test or chi-square test, where appropriate.

Curved/linear regression analysis will be performed to assess the correlations between each outcome and stress as well as emotions. As it is common practice, results of Likert-like scales will be treated as interval-measures and thereby analyzed by using parametric tests.^{36,37}

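### The primary ANCOVA leaves out the initial-test OGRS score, a covariate that is already rated for everyone and would improve precision for one degree of freedom

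*SAP*

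**What the plan says.** **Outcome.** Protocol 7.1.1 compares the groups on retention of non-technical skills, "specified as the difference in performance between the initial and the retention test, will be our primary outcome". The SAP heading for the primary outcome also speaks of a difference in retention.

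**Model.** Protocol 7.3 states that "ANCOVA will be used to analyze the outcome parameters using the level of training" and specialty type as covariates, and that "Group assignment (unexpected death, alive) will be used as the independent variable". The SAP gives the dependent variable as "Dependent variable: OGRS score (total score)", the factor as "Independent variable: Death vs. survival", and the same two covariates. The initial-test score is a covariate in neither document.

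**Availability of the initial score.** Protocol 6.1.2 has the same two blinded raters score every recorded scenario. Section 6 (Both Phases) says that the two versions of the scenario run identically until the last two minutes and that raters do not see the ending. Section 6.3 blinds participants to group and scenario at the briefing.

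**Sample size.** Protocol 7.2 uses d = 0.8, two-sided 5%, 80% power and an ANCOVA r² of 0.12. It arrives at 46 participants, and 56 after attrition.

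**The concern.** A participant's performance at the first test is a natural predictor of performance at the second, and here it is measured with the same instrument and the same raters. A change score uses it only by subtraction, which fixes its coefficient at 1. A retention-only score ignores it, which fixes the coefficient at 0. ANCOVA estimates the coefficient and, apart from the lost degree of freedom, does at least as well as either. With about 46 evaluable participants, precision and protection against chance imbalance at the initial test are worth having.

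A smaller matter sits beside this. The SAP line for the primary model names neither the change nor the test occasion, although each participant has two OGRS totals. The same SAP is explicit elsewhere: "Dependent variable: Change in cortisol concentration (versus baseline) at a given time point" for cortisol and "Time points: Initial and retention" for emotions. The factor also carries no occasion in the SAP, while outcomes are switched at the retention test so that "each participant will be exposed to simulation death in the study once".

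**Working it through.** **1. The plan's own figure.** Inputs from Protocol 7.2: d = 0.8, two-sided alpha 0.05, power 0.80, r² = 0.12. A two-sample t-test needs 26 per group (power 0.807), 52 in total. Then 52 × (1 − 0.12) = 45.76, rounded up to 46. For attrition, 46 × 1.2 = 55.2, rounded up to 56. Both stated numbers reproduce, so the point does not rest on an error in the sample size.

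**2. Assumptions.** The correlation rho between initial and retention OGRS scores is not in the documents, so 0.35, 0.5 and 0.7 are shown. The value 0.35 is close to √0.12 = 0.346, which is what r² = 0.12 would imply if it referred to the initial score. The SD is taken as equal at both tests (set to 1), with a common slope in both groups and, at first, strata that explain nothing.

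**3. Residual variance per participant.**
- Retention score alone: 1
- Change score: 2(1 − rho)
- Adjusted for the initial score: 1 − rho²

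**4. Participants needed relative to the adjusted model.**
- Change / adjusted = 2(1 − rho)/(1 − rho²) = 2/(1 + rho)
- Retention-only / adjusted = 1/(1 − rho²)

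| rho | change / adjusted | in place of 46 | retention-only / adjusted | in place of 46 |
|---|---|---|---|---|
| 0.35 | 2/1.35 = 1.48 | 68 | 1/0.8775 = 1.14 | 52 |
| 0.5 | 2/1.5 = 1.33 | 61 | 1/0.75 = 1.33 | 61 |
| 0.7 | 2/1.7 = 1.18 | 54 | 1/0.51 = 1.96 | 90 |

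These ratios do not depend on which SD d = 0.8 refers to.

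**5. Sensitivity to the strata.** Suppose the stratification factors explain 12% of the variance at each test, equally, so that they cancel from the change score. The within-stratum correlation is then (rho − 0.12)/0.88 = 0.26, 0.43, 0.66. The excess for the change score becomes 59%, 40%, 21%, and for retention-only 7%, 23%, 77%. The conclusion is the same.

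**6. Power with 46 analysed** (noncentral t, 23 per group, strata explaining nothing, 42 df, or 41 with the initial score). Protocol 7.2 does not say which SD scales d, so both are shown.

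| rho | d on single-test SD: change / retention-only / adjusted | d on change SD: change / retention-only / adjusted |
|---|---|---|
| 0.35 | 64 / 76 / 81% | 76 / 86 / 90% |
| 0.5 | 76 / 76 / 86% | 76 / 76 / 86% |
| 0.7 | 93 / 76 / 96% | 76 / 54 / 82% |

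If d is on the change SD and the strata explain 12% of the change itself, the planned change analysis reaches 81%, which meets the plan. That is a different assumption from step 5, and the two sets of figures should not be combined.

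**7. Either dependent variable will do.** Once the initial score is a covariate, replacing the retention score by the change score lowers the coefficient of the initial score by exactly 1 and leaves the group effect and its standard error unchanged.

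**8. Chance imbalance.** With 23 per group the SE of the initial difference is √(2/23) = 0.295 SD. An imbalance of 0.4 SD would shift the retention-only estimate by 0.4 × rho = 0.14, 0.20, 0.28 SD. It would shift the change estimate by 0.4 × (1 − rho) = 0.26, 0.20, 0.12 SD in the opposite direction. The adjusted model removes this shift.

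**The case against.** The two documents agree on the covariates, and Protocol 7.3 gives a reason: these are the stratification factors. A change score adjusted for strata is a valid 5% test under randomisation, with the same expected group difference as the alternatives. All of this stands. Omitting the initial score is a less efficient choice and not an error.

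Randomisation takes place just before the initial scenario, so one may ask whether the initial score is a proper baseline. The groups' scenarios do not differ until the last two minutes, the ending is hidden from raters, and participants are blinded at the briefing. On those terms the score is effectively a pre-divergence measurement. A change score relies on the same condition.

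Three stronger readings are tempting and are not supported:
- **That the SAP replaces the protocol's outcome with another.** Protocol 7.1.1 fixes the change, the SAP heading is consistent with it, and the SAP line is silent rather than contradictory. Likewise, Protocol 7.3 settles that the factor is group assignment and not the outcome on the day.
- **That the open wording inflates the false-positive rate.** That would require running both the change and the retention-only analysis and counting either. Nothing in the documents proposes this.
- **That the trial is underpowered.** The 46 reproduces, and whether the planned analysis reaches 80% depends on a correlation and an SD basis that the documents do not give.

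**Conclusion.** The point holds as a nearly free improvement to the primary model. For the assumed correlations of 0.35 to 0.7 with equal SDs, leaving out the initial score costs the equivalent of 48% down to 18% more participants for a change score, and 14% up to 96% more for a retention-only score. The direction does not depend on these values: with a common slope, the adjusted residual variance is no larger than that of either alternative for any SDs. The size does depend on them. Validity is not in question, and no shortfall against the stated power is demonstrated. The incomplete SAP line is a matter of clarification only.

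**What to change.** In Protocol 7.3 and in the SAP's primary model:
- Add the initial-test OGRS total score as a covariate beside the two stratification factors.
- Keep the change score of Protocol 7.1.1 as dependent variable, or use the retention-test score; the group effect is identical. Write the choice into the SAP line, with the test occasion or occasions, so that it matches Protocol 7.1.1.
- Name the factor in the SAP as randomised group, that is, the outcome assigned at the initial test.

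Apply the same form to retention on the 18-point checklist. Protocol 7.1.2 also lists checklist performance, which needs its own line because this model covers only retention.

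Two short statements would help but are secondary: which covariate supplies r² = 0.12, and that the rated initial video stops before the groups diverge.

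The cost is wording and one degree of freedom. No new data are needed.

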6.1.3 Stress Assessment

Acute stress will be assessed by means of salivary cortisol, the State-Trait Anxiety Inventory (STAI) and questionnaire aligned with the cognitive appraisal theory.^{4,5,10,25}

Salivary Cortisol

The activation of the hypothalamic-pituitary-adrenal axis as surrogate for psychological stress will be measured using salivary cortisol levels that show a close to linear relationship to plasma cortisol levels.^{4,5,26} Cortisol levels will be measured in both simulation tests (initial test and retention test). Salivary cortisol peaks at 20 to 40 minutes after the onset of a stressor.⁴ In order to approach cortisol kinetic, 5 cortisol samples will be obtained per participant per scenario: when participants arrive at the simulation center (sample 0), just before each scenario (sample 1), immediately at the end of the each scenario (sample 2), 30 minutes after the start of the scenario (sample 3), and at the end of the debriefing phase (sample 4). The cortisol sampling schedule for the initial and the retention test will be identically, resulting in a total of 10 cortisol samples per participants (see Appendix D). A roll shaped synthetic saliva collector (Salivette for Cortisol testing, Starstedt, Montreal, Quebec, Canada) will be used and will be frozen at -20°C until analysis using an ELISA technique at the Technische Universität Dresden, Germany.

State-Trait Anxiety Inventory (STAI)

To evaluate acute and subjective stress the standardized test battery of the STAI will be used. With STAI state anxiety at the very given moment can be measured using 20 statements to which the participants agree or disagree on a four point Likert-like scale (1 – not at all, 4 very much so). The sub scores are summed up and provide a sensitive basis for acute changes in anxiety related to stressful simulation.^{10,25} STAI will be assessed after the resting phase before each scenario and immediately after the debriefing of the initial and the retention scenario.

Cognitive Appraisal

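### The SAP's cortisol regression over time makes no provision for repeated samples from one person, so its tests of training level and specialty would be too liberal if samples are pooled; no joint arm-by-time test is planned

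*SAP*

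**What the plan says.** For cortisol, the SAP (Secondary Outcome 2, Measure 1) lists three analyses:

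- An ANCOVA with arm as the independent variable and training level and specialty as covariates. Its dependent variable is "Change in cortisol concentration (versus baseline) at a given time point (for each time point".
- A regression, described as "Linear regression to determine the effects of covariates (Junior vs. senior; Acute vs. non-acute) on change in cortisol concentration over time". It is qualified by "Separated into “death” and “survival” groups" and by "Change in cortisol concentration will be established using the baseline reading of each participant on each day of the study (time point 1".
- Unpaired t-tests between the arms at each time point.

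The regression item names no participant effect, covariance structure or robust standard error. STAI (Measure 2) follows the same plan, with the STAI score replacing the cortisol change. For emotions (Secondary Outcome 3) the SAP names a "Repeated measures ANCOVA".

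Protocol section 6.1.3 states that "5 cortisol samples will be obtained per participant per scenario", "resulting in a total of 10 cortisol samples per participants". It schedules STAI twice per session, before the scenario and after the debriefing.

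**The concern.** Two of the three cortisol analyses are explicitly done one time point at a time. Only the regression is on change *over time*, which points to one model holding all samples. Each person gives four changes per session, and all four subtract the same baseline reading, so they are correlated. A plain linear regression would count them as four independent people. The SAP names a repeated-measures method for emotions but none here, so the text as written permits the invalid fit.

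At stake are the p-values for training level and specialty as predictors of the cortisol response, and to a lesser degree of STAI. Fitting each arm separately also means that this analysis, the only cortisol analysis that spans the time points, says nothing formal about whether the time course differs by arm.

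**Working it through.** **Inputs.**
- Five samples per session give 5 − 1 = 4 changes per person per session, and 8 over both days (protocol 6.1.3).
- 46 evaluable participants (protocol 7.2) at 1:1 (6.2) give about 23 per arm; 56 recruited give 28.
- The within-person correlation ρ of the changes is not in the documents. I assume 0.3, 0.5 and 0.7.

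**The plan's own figure.** The documents give no figure for this regression, so only the number of people carries over. An unadjusted t-test needs 52 participants for d = 0.8. 52 × (1 − 0.12) = 45.8, hence 46, and 46 × 1.2 = 55.2, hence 56. Both stated numbers reproduce.

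**Why 0.5 is a reasonable middle value.** Suppose the raw samples have equal variance σ² and equal correlation r. Each change from the shared baseline has variance 2σ²(1 − r), and two changes have covariance σ²(1 − r). Their correlation is therefore 0.5 whatever r is.

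**Covariates that vary between people, 4 values each.** The true standard error divided by the ordinary least squares (OLS) one is √(1 + 3ρ). The type I error of a nominal 5% test is about 2(1 − Φ(1.96/factor)). At 23 per arm, each fit would treat 23 × 4 = 92 rows as 92 people.

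The formula was checked by simulation under the null: 3,000 runs per setting, one arm of 23 or 28 people, samples at 10, 30, 45 and 50 minutes, and pooled OLS with both covariates and linear time.

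| ρ | SE factor | Type I, formula | Type I, simulated (23 / 28 people) | Time slope: true SE / OLS SE (23 / 28) |
|---|---|---|---|---|
| 0.3 | √1.9 = 1.38 | 15.5% | 15.7% / 17.0% | 0.84 / 0.86 |
| 0.5 | √2.5 = 1.58 | 21.5% | 21.7% / 22.7% | 0.71 / 0.73 |
| 0.7 | √3.1 = 1.76 | 26.6% | 28.8% / 28.1% | 0.59 / 0.57 |

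Analysing one mean per person in the same simulated data brought the type I error back to 4.3% to 5.8%.

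**Time slope.** The last column shows the opposite error. OLS overstates this standard error, and the simulated type I error for the slope was 0% to 2.3%.

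**Both days pooled, 8 values.** With equal correlation across all eight, the factor √(1 + 7ρ) is 1.76, 2.12 and 2.43, and the type I error is about 27% to 42%. With the across-day correlation set at half the within-day value, simulation gave about 22%, 31% and 36%.

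**STAI, 2 values per session.** √(1 + ρ) = 1.14, 1.22 and 1.30, so the type I error is about 9%, 11% and 13%.

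**The case against.** **Pooling is inferred.** The SAP does not say that the time points enter one model, and a regression at each time point would have no clustering problem. This stands as a caveat. Against it, the neighbouring items say per time point and this one does not, and a per-time-point version would largely repeat the covariate terms of the ANCOVA. If it is what was meant, the SAP should say so.

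**A reader might infer that the plan cannot compare the arms.** The documents do not support that. The ANCOVA and t-tests compare them at every time point, using one value per person, and within-person correlation does not bias those tests. The regression's stated aim is covariate effects. What is absent is a joint arm-by-time test.

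**A reader might infer that all standard errors are understated.** They are not; the slope's is overstated. A covariate-by-time term, if *over time* means that, is also a within-person contrast and would err in the same direction as the slope under equal correlation.

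**A reader might infer that a straight line is forced through a rise and fall.** The SAP names no functional form for time. Protocol 6.1.3 puts the peak 20 to 40 minutes after stressor onset. On the SAP's clock, 45 minutes is 30 minutes after the scenario starts, so the last sample, at 50 minutes, is 35 minutes after. That is still inside the peak window.

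**The consequence is limited.** Effects of training level and specialty on cortisol are not among the objectives in protocol section 4, and section 8.2 calls all aspects hypothesis generating. This stands and sets the weight of the point. It does not make a test with a 20% error rate a sound source of hypotheses.

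**Conclusion.** The point holds for this regression on its natural, pooled reading. The standard errors for training level and specialty would be too small by about 1.4 to 1.8 times, and nominal 5% tests would run at about 15% to 29% per session. For STAI the rate is about 9% to 13%. The slope's standard error would be too large. These sizes rest on an assumed within-person correlation of 0.3 to 0.7, equal across samples. The higher figures for both days pooled also need an assumption about correlation over three months, so they are not relied on. No joint arm-by-time test is planned, and separate fits per arm cannot supply one.

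The point is confined to a secondary outcome. The planned arm comparisons at single time points remain valid in this respect.

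**What to change.** Replace the per-arm cortisol regressions with one linear mixed model per session:

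- **Outcome:** same-day change from baseline, as the SAP defines it.
- **Fixed effects:** arm, sample time (categorical), arm-by-time, training level, specialty, each of these two by time, and initial-day baseline cortisol. The initial-day value is taken on arrival, before randomisation; the retention-day baseline is not, so it should not be a covariate.
- **Within-person correlation:** a participant random effect or an unstructured covariance, with a small-sample degrees-of-freedom correction.

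The covariate-by-time terms answer the SAP's own question, and the arm-by-time terms supply the missing joint test. The arm contrasts at each sample should be read from this model in place of the unadjusted t-tests. If the per-time-point ANCOVA is kept, the SAP should say which result is reported as the arm comparison. The model gives covariate effects common to both arms; if effects within each arm are wanted, arm-by-covariate terms must be added.

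For STAI, use the same structure with its two measurement times. In the initial session omit the baseline covariate, because the pre-scenario score is already one of the two outcomes.

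The cost is a few lines of SAP text and more parameters in a small sample. For cortisol there are 1 + 1 + 3 + 3 + 1 + 1 + 3 + 3 + 1 = 17 fixed effects including the intercept, against 46 × 4 = 184 values per session. The primary analysis, sample size and data collection do not change.

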4.2 Secondary Objectives

Our secondary objectives are:

- (i) To assess if unexpected death of a simulated patient is associated with an impaired retention of technical resuscitation skills.
- (ii) To examine if unexpected death of a simulated patient is associated with future higher stress levels and stronger emotions during simulated crisis.
- (iii) To investigate the relationship between stress levels as well as emotions and future performance in crisis.

We furthermore hypothesize, that simulated death will lead to higher stress levels as well as more negative emotions and will thereby impact the ability to retain critical skills.

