7.2 Sample size considerations

A priori sample size calculation was performed on the basis of an estimated Cohen's *d* effect size of 0.8, which is considered large and acceptable for a teaching intervention.³³ We aim at a two-tailed level of significance of $p < 0.05$ and a power of 0.8. Using the recommended sample size estimation approach for ANCOVA³⁴ with an estimated r^2 of 0.12, derived by a previous, not now published trial ([name] et al, Learning crisis resource management: Practice versus observing, CAS 2013 Abstract 1653689, accessible at <http://www.cas.ca/English/AM-Abstracts-2013>), a number of 46 participants would be needed. In order to account for an estimated attrition rate of 20% we need to recruit 56 participants. G*Power for MAC (version 3.12, Düsseldorf, Germany) was used for sample size calculations.

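### Cortisol is analysed as unadjusted same-day change: the initial test leaves out a pre-randomisation baseline already collected, and the retention test never compares arrival cortisol between groups

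*SAP*

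**What the plan says.** In the SAP, under Secondary Outcome 2, Measure 1, the cortisol ANCOVA is specified as "Dependent variable: Change in cortisol concentration (versus baseline) at a given time point (for each time point"). Its only covariates are junior/senior and acute/non-acute. The unpaired t-tests use the same change variable. The one definition of change stands under the regression item: "Change in cortisol concentration will be established using the baseline reading of each participant on each day of the study (time point 1"). Because it refers to each study day, the retention analysis subtracts the retention-day arrival sample.

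Protocol 6.1.3 places sample 0 at arrival and uses the same five-sample schedule on both days. Protocol 6 (Initial Test) and 6.2 place the opening of the allocation envelope after the resting period, immediately before the scenario briefing. Initial-day sample 0 is therefore a pre-randomisation value. The retention test follows 3 months later, so its sample 0 is a post-randomisation value.

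Secondary objective (ii) in Protocol 4.2 is: "To examine if unexpected death of a simulated patient is associated with future higher stress levels and stronger emotions during simulated crisis". At retention the mannequin outcome is switched, so it is the control group that meets the death (Protocol 6, Retention Test).

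**The concern.** The two test days raise different problems.

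- **Initial test.** An unadjusted change score fixes the slope on baseline at exactly 1. Estimating that slope is normally at least as precise. The baseline is already collected and is a valid covariate, so precision may be given away in a trial whose own limitations section (Protocol 8.2) says it is limited by sample size.
- **Retention test.** If having met a simulated death makes trainees more stressed on returning to the same setting, part of that response could already be present at arrival. Subtracting the arrival sample removes that part from all later contrasts. Change at time point 1 is zero by construction, so the cortisol plan has no other place where it could show. At stake is whether cortisol can speak to carried-over stress under objective (ii).

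**Working it through.** **The plan's own figure.** The documents give no sample size or power for cortisol. The figure in Protocol 7.2 is for the primary outcome. A two-sample t-test with d = 0.8, two-sided 0.05 and power 0.80 needs 26 per arm, or 52. Then 52 × (1 − 0.12) = 45.76, so 46, as stated ("a number of 46 participants would be needed"). Next, 46 × 1.2 = 55.2, so 56, as stated. These figures are not in dispute here; 46 evaluable (23 per arm) is used below.

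**Assumed inputs.** Cortisol SDs, correlations and effect sizes are not in the documents. All variances are in units of the squared outcome SD, and the 0.8 SD effect is borrowed from the primary outcome.

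**Step 1: initial test, equal variances.** With correlation ρ between baseline and later sample:

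- Var(change) = 2(1−ρ)
- Var(ANCOVA on baseline) = 1−ρ²
- Ratio = (1+ρ)/2, so the reduction is (1−ρ)/2

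| ρ (assumed) | Var change | Var ANCOVA | Reduction | Power, change | Power, ANCOVA |
|---|---|---|---|---|---|
| 0.3 | 1.40 | 0.91 | 35% | 61% | 79% |
| 0.5 | 1.00 | 0.75 | 25% | 76% | 86% |
| 0.7 | 0.60 | 0.51 | 15% | 93% | 96% |
| 0.9 | 0.20 | 0.19 | 5% | over 99% | over 99% |

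The power columns use the noncentral t and already charge ANCOVA the extra degree of freedom. Below ρ = 0.5 the change score has a variance above 1, so it is less precise than the raw level.

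**Step 2: initial test, unequal variances.** The gain depends on how far the true slope is from 1. With baseline SD 1, in-scenario SD 2 and ρ = 0.5, Var(change) = 4 + 1 − 2 × 0.5 × 2 = 3 and Var(ANCOVA) = 4 × (1 − 0.25) = 3. The slope is then 0.5 × 2 = 1 and nothing is gained.

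**Step 3: retention test, what each contrast estimates.** Let the earlier death shift arrival cortisol by a and a later sample by b. Let c be the control group's response to its own new death, in samples late enough to reflect it.

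- Planned change, sample not yet affected by the new death: b − a
- Planned change, late sample: b − a − c
- Arrival level: a (the planned change here is always zero)
- Pre-scenario level: b
- Late sample, level: b − c

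The two scenarios differ only in the final two minutes (Protocol 6, Both Phases), and cortisol peaks 20 to 40 minutes after a stressor begins (Protocol 6.1.3). The end-of-debriefing sample is therefore the one most clearly exposed to c. Arrival and pre-scenario samples are free of it. The SAP sets the first to zero and compares the second with a reading nominally 10 minutes earlier.

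**Step 4: retention test, size if a shift exists.** A simulation of 5,000 runs per scenario with within-day correlation 0.6, between-day correlation 0.4, a total effect of 0.8 SD and c = 0 gave these mean estimates and power:

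| Share of effect present at arrival | Same-day change | Level, initial-day sample 0 as covariate |
|---|---|---|
| All | 0.00, 5% | 0.80, 82% |
| Half | 0.40, 32% | 0.80, 82% |
| None | 0.80, 84% | 0.80, 82% |

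Using the retention-day arrival sample as a covariate instead does not repair this, because it conditions on a post-randomisation value. It recovers only (1−ρ)a: with the whole effect at arrival, (1 − 0.6) × 0.8 = 0.32, with 23% power.

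**Step 5: retention test, precision.** The variance with the initial-day covariate is 1 − 0.4² = 0.84. Same-day change has 2(1 − 0.6) = 0.80, or 2(1 − 0.7) = 0.60 at within-day 0.7. The saving in Step 1 does not carry over; at within-day 0.7 the initial-day covariate has 0.84/0.60 = 1.40 times the variance.

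**The case against.** The strongest defence is that same-day change is a legitimate estimand. Objective (ii) concerns stress during a simulated crisis, and reactivity within the visit is a fair reading of that. It also removes between-day differences, such as testing at different hours within the 11 AM to 8 PM window. It is unbiased at the initial test, and with no arrival shift it is unbiased at retention for samples taken before the new death can register. All of this stands, and it is why change should be kept under its own label rather than removed.

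The defence also limits how far the point may be pushed. A reader might infer any of the following, and the documents do not support them.

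- **That the plan hides the effect on future stress.** Masking needs a real arrival rise 3 months later. The documents offer no evidence of one. Protocol 6.4.2 cites earlier studies in which stress returned to baseline by the end of the scenarios; that says nothing direct about 3 months, but it does not suggest a carry-over. Reactivity beyond any arrival shift stays visible. STAI is analysed as a score and is taken before each scenario. Appraisal is a ratio, taken after each briefing and compared between groups. Carried-over stress can appear in both.
- **That the 15% to 35% saving applies at both tests.** It applies to the initial test, for assumed correlations of 0.3 to 0.7 and equal variances. Step 5 shows that it does not hold at retention.
- **That analysing levels isolates future stress in every retention sample.** The late samples still carry the control group's new death.
- **That the SAP removed a baseline covariate.** Protocol 7.3 lists only the same two strata.

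**Conclusion.** The point holds in a limited form, for a secondary outcome.

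At the initial test the plan omits a valid baseline covariate that it already has. The variance saving is 35% to 5% for assumed ρ from 0.3 to 0.9 under equal variances. It shrinks or vanishes if in-scenario variance is larger and brings the slope close to 1. Apart from the one degree of freedom, adjustment should not be worse than change in large samples.

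At the retention test the gap is one of coverage. Arrival cortisol is post-randomisation, is subtracted from everything after it, and is never compared between groups, although objective (ii) asks about future stress levels. Whether this costs anything depends on an arrival shift that the documents neither show nor rule out: under the Step 4 assumptions, power for a 0.8 SD effect is 84% with no shift, 32% with half the effect at arrival and 5% with all of it. The flat statement that the retention analysis is biased toward no effect goes further than the documents allow. The primary outcome, STAI and appraisal are not affected.

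**What to change.** In the SAP, Secondary Outcome 2, Measure 1:

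1. At the initial test, add initial-day sample 0 as a covariate alongside the two strata.
2. At the retention test, compare arrival and pre-scenario cortisol levels between groups, adjusted for initial-day sample 0 and the two strata. Name this as the cortisol analysis of carried-over stress for objective (ii). Do not adjust these levels for the retention-day arrival sample.
3. Keep same-day change as a labelled reactivity analysis. State that post-scenario retention samples may also reflect the control group's new simulated death.

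The cost is SAP wording, one degree of freedom per model and two further group comparisons at retention. No new data are needed. The price to accept is precision at retention: the initial-day covariate may do no better than same-day change, or worse (0.84 against 0.80 or 0.60 under the assumed correlations). For the arrival sample there is no such trade-off, because its planned change is always zero.
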